#### **Statistical Methods:**

##### Sample size

- As this is the first in human clinical study and no clinical data is available, no formal sample size calculations have been performed for both parts of the clinical study.
- The sample size has been selected for practical considerations and is based upon experience from similar past clinical study designs.
- The selected number of subjects is considered sufficient to achieve the clinical study objectives.

##### Pharmacokinetics

- In the SAD part, proportionality between the dose administered and the PK parameters will be assessed by means of a mixed-effects analysis of variance (ANOVA) model with cohort and dose (nested within cohort) as fixed effects, and subject (nested within cohort) as random effect in the model on the following ln-transformed ARGX-113 parameters:  $C_{\max}/\text{dose}$ ,  $C_{72\text{h}}/\text{dose}$ ,  $\text{AUC}_{0-72\text{h}}/\text{dose}$ ,  $\text{AUC}_{\text{inf}}/\text{dose}$ , total Ae %,  $\text{CL}_{\text{R}}$  and  $t_{1/2,\lambda_z}$  (if possible). In case of significant dose effect observed on these parameters, comparison between doses will be performed using Tukey's test. As  $t_{\max}$  is a discrete variable dependent on selected blood sampling times, dose effect will be assessed using a non-parametric Kruskal-Wallis test and in case statistically significant, applying Wilcoxon's rank sum test with Moses' 90% confidence intervals for pairwise comparisons.
- In the MAD part, proportionality between the dose administered and the PK parameters will be assessed, when appropriate, by means of a mixed effects model on ln-transformed ARGX-113 ( $C_{\max}/\text{dose}$ ,  $C_{72\text{h}}/\text{dose}$  or  $C_{168\text{h}}/\text{dose}$ ,  $\text{AUC}_{72\text{h}}/\text{dose}$  or  $\text{AUC}_{168\text{h}}/\text{dose}$ , and  $t_{1/2,\lambda_z}$ ) with random subject effect and with day, dose and dose\*day interaction as fixed effects. The dose effect on ln-transformed  $R_{\text{ac}}$  will be evaluated from a mixed effect analysis of variance with dose as fixed effect and subject as random effect. As  $t_{\max}$  is a discrete variable dependent on selected blood sampling times, the dose effect will be assessed using a non-parametric Wilcoxon's rank sum test plus 90% CIs. The day effect will be tested using the non-parametric Wilcoxon's signed ranks test.

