### **Overview of Study Design:**

This study is a First-in-Human, Phase I, randomized, double-blind, placebo-controlled, single-center study evaluating single (SAD) and multiple (MAD) ascending intravenous (IV) doses of ARGX-113 in healthy subjects. The study will consist of 2 parts.

Up to 68 healthy male subjects or healthy female subjects of non-childbearing potential will be selected according to the inclusion and exclusion criteria, i.e., up to 36 subjects in the SAD study (Part 1) and up to 32 subjects in the MAD study (Part 2). The SAD study will contain up to 6 cohorts of 6 subjects each, with the 6th cohort being optional (to be added if no plateau in IgG reduction is reached and if there are no safety issues with the prior dose level). The MAD study will contain up to 4 cohorts of 8 subjects each.

ARGX-113 or placebo will be administered intravenously by an infusion over 2h. A staggered approach will be observed within all dose levels. For the SAD study, for each cohort, 2 sentinel subjects will be dosed followed by 4 subjects 24h later. For the MAD study, dosing will be done in 2 subgroups, 4 subjects in each subgroup. This will apply to all MAD cohorts (8 subgroups in total). An interval of at least 14 days between dosing of the first subject of each SAD and MAD dose level will be observed.

A schematic overview of the study design for Part 1 and Part 2 is presented below:

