**Part 1: SAD**

Cohort	N	Dose	Drug administration
1a	1:1	0.2 mg/kg	ARGX-113 or placebo x 1 day
1b	3:1	0.2 mg/kg	ARGX-113 or placebo x 1 day
2a	1:1	2.0 mg/kg	ARGX-113 or placebo x 1 day
2b	3:1	2.0 mg/kg	ARGX-113 or placebo x 1 day
3a	1:1	10 mg/kg	ARGX-113 or placebo x 1 day
3b	3:1	10 mg/kg	ARGX-113 or placebo x 1 day
4a	1:1	25 mg/kg	ARGX-113 or placebo x 1 day
4b	3:1	25 mg/kg	ARGX-113 or placebo x 1 day
5a	1:1	50 mg/kg	ARGX-113 or placebo x 1 day
5b	3:1	50 mg/kg	ARGX-113 or placebo x 1 day
6a 	1:1	TBD	ARGX-113 or placebo x 1 day
6b 	3:1	TBD	ARGX-113 or placebo x 1 day

The a-group refers to the sentinel subjects and the b-group refers to the remainder of the subjects in the cohort. Two sentinel subjects will be dosed, followed by 4 subjects 24h later. An interval of at least 14 days between dosing of the first subject of each SAD dose level will be observed.

active:placebo

Doses are based on weight at Day -1. These doses may be adapted according to the safety, PK and PD data obtained during the study.

Optional cohort, to be conducted as needed. Dose level to be determined (TBD).

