**Criteria for Evaluation:**

Safety

- Safety signals will be assessed to determine dose escalation. Blinded safety data review meetings (Safety Committee), consisting of (but not limited to) the sponsor's Medical Monitor and the Principal Investigator will be conducted after each cohort to confirm the decision to move forward with each dose escalation.
- If safety signals are detected, including observed toxicities and/or based on the available pharmacodynamic (PD) effect, the Safety Committee can advise that the dose in the following cohort can be repeated, replaced with an intermediate dose, or decreased (Part 1).
- The decision to repeat, decrease, increase, or select an intermediate dose will be made upon satisfactory review of blinded safety data (up to at least Day 5 for Part 1: SAD and up to at least 5 days post last dose for Part 2: MAD) in at least 5 subjects from the preceding dose level, as well as blinded PK and PD data obtained on an ongoing basis as available, by the Safety Committee.

Pharmacokinetic

Individual subject plasma ARGX-113 concentrations will be used to derive PK parameters using a non-compartmental method.

The following PK parameters will be estimated, where appropriate:  $C_{max}$ ,  $t_{max}$ ,  $C_{72h}$  ( $C_{168h}$ ),  $AUC_{0-t}$ ,  $AUC_{0-72h}$  ( $AUC_{0-168h}$ ),  $AUC_{inf}$ ,  $t_{1/2,\lambda,z}$ ,  $CL$ , and  $V_z$ . Cumulative amount excreted ( $A_e$ ) in urine for each collection interval and in total will be calculated in absolute and % of administered dose values.  $CL_R$  and  $CL_{CR}$  (to check urine collection compliance) will also be presented. In addition, after multiple dose administrations,  $R_{ac}$  will be calculated.

Other PK parameters may be calculated as appropriate.

---

---

Dose normalized parameters ( $C_{\max}/\text{dose}$ ,  $C_{72\text{h}}/\text{dose}$ ,  $C_{168\text{h}}/\text{dose}$ ,  $\text{AUCs}/\text{dose}$ ,  $\text{Ae}\%$ ) will be assessed. Additional PK parameters may be calculated as appropriate.

Creatinine analysis will be performed in urine to check urine collection compliance. Creatinine clearance ( $\text{CL}_{\text{CR}}$ ) will be calculated for each fraction.

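### The Part 1 dose-proportionality model nests dose within cohort, but each cohort has only one dose, so the dose effect that triggers Tukey's comparisons has 0 degrees of freedom

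*Protocol*

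**What the plan says.** In the Protocol synopsis, Statistical Methods, Pharmacokinetics, the Part 1 (SAD) model is a "mixed-effects analysis of variance (ANOVA) model with cohort and dose (nested within cohort) as fixed effects, and subject (nested within cohort) as random effect". It applies to ln-transformed Cmax, C72h, AUC0-72h and AUCinf, each divided by dose, and to total Ae %, renal clearance and terminal half-life. The follow-up is conditional: "In case of significant dose effect observed on these parameters, comparison between doses will be performed using Tukey's test".

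The design is set out in two other places.

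- Overview of Study Design: "The SAD study will contain up to 6 cohorts of 6 subjects each", with a total of "up to 36 subjects in the SAD study (Part 1) and up to 32 subjects in the MAD study (Part 2").
- Part 1: SAD table: cohorts 1 to 5 are assigned 0.2, 2.0, 10, 25 and 50 mg/kg, and the optional cohort 6 has a dose still to be set. Every row reads "ARGX-113 or placebo x 1 day". The a and b rows of a cohort carry the same dose: "The a-group refers to the sentinel subjects and the b-group refers to the remainder of the subjects in the cohort".

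Criteria for Evaluation adds that "Individual subject plasma ARGX-113 concentrations will be used to derive PK parameters using a non-compartmental method", so a single-dose subject yields one value of each parameter.

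**The concern.** A nested term of this kind makes sense when a cohort receives several dose levels, for instance over successive periods, and each subject is measured more than once. Nothing in the Protocol describes that for Part 1. There is no crossover, no second dosing period and no cohort with two active doses. Six cohorts of six subjects account for all 36 places, so no subject is counted in two cohorts.

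Two separate faults follow. Once cohort is fitted, dose within cohort has nothing left to explain. Separately, a random subject effect with one observation per subject duplicates the residual error. The second fault does not cause the first.

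What is at stake is the formal dose-proportionality assessment of Part 1, which serves the secondary PK objective. Its pairwise step waits for a significant dose effect that the stated model cannot deliver. An analysis plan that copies the model inherits the fault, and one that departs from it disagrees with the Protocol.

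**Working it through.** The Protocol gives no degrees of freedom, power or sample-size derivation for this model, so there is no stated figure to reproduce. The check is a count of estimable terms.

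**Inputs**

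- Cohorts: 5 planned plus 1 optional (Overview of Study Design).
- Doses per cohort: one (Part 1: SAD table).
- Active subjects per cohort: 1 of the 2 sentinels (1:1) plus 3 of the other 4 (3:1), so 1 + 3 = 4. Only these subjects have ARGX-113 parameters.
- Observations: one per active subject and parameter, so n = 5 × 4 = 20, or 6 × 4 = 24 with the optional cohort.

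**Step 1: degrees of freedom for dose**

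df[dose(cohort)] = rank[1, cohort, dose(cohort)] − rank[1, cohort]

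| Design | n | Rank with cohort | Rank adding dose(cohort) | df cohort | df dose(cohort) |
|---|---|---|---|---|---|
| 5 cohorts | 20 | 5 | 5 | 4 | 0 |
| 6 cohorts | 24 | 6 | 6 | 5 | 0 |

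Each cohort-by-dose indicator is identical to a cohort indicator, so the nested term adds no column.

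**Step 2: the random subject term**

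With one value per subject, Var(y) = σ²(subject) + σ²(residual) for each observation, with no covariance between observations. The likelihood depends only on the sum. On 20 simulated values with the total variance held at 1, the log-likelihood (without its constant) is −2.62 for subject/residual splits of 0/1, 0.5/0.5 and 0.9/0.1. Counted as fixed indicators, the subjects use all remaining information: 20 − 5 = 15 residual df before subject, 0 after. With six cohorts it is 24 − 6 = 18 before and 0 after.

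**Step 3: readings that might rescue the dose term**

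- *Sub-groups a and b counted as cohorts.* Cohort has 9 df and dose(cohort) still 0, because both sub-groups of a cohort share a dose.
- *A dose repeated in a later cohort*, which Criteria for Evaluation permits. With six cohorts and one repeat, cohort has 5 df and dose(cohort) still 0.
- *Placebo treated as a dose level.* With 5 × 6 = 30 subjects, dose(cohort) would have 5 df. But the responses are ARGX-113 parameters, most of them divided by dose, and placebo subjects have none.

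**Step 4: the model with dose alone**

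| Design | df dose | df residual | Critical F at 5% |
|---|---|---|---|
| 5 doses, n = 20 | 4 | 15 | 3.06 |
| 6 distinct doses, n = 24 | 5 | 18 | 2.77 |

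The 5% level is an assumption, since the synopsis gives no significance level for this test.

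**The case against.** The strongest reply is that nothing is lost. When every cohort has a different dose, cohort and dose are the same factor. The between-dose contrasts then sit wholly in the cohort term, and the cohort test is the one-way dose ANOVA on 4 and 15 df. The redundant random term leaves the estimated means unchanged. Safety and tolerability are the primary objectives and are analysed descriptively. Neither the sample size nor dose escalation rests on this model.

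Most of that stands, and it limits the severity. It does not remove the error. Reading the cohort test as the dose test is a substitution that the text does not make. It also fails if a dose is repeated: with six cohorts and one repeat, cohort has 5 df while dose alone has 4 df (19 residual), so the two tests differ.

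A reader might infer more than the Protocol supports, in four ways.

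- *That Part 1 cannot address proportionality.* The fault is in the model, not in the design.
- *That the analyst must choose a new model after seeing data.* The aliasing is visible before any data exist, and an analysis plan not shown here may already deal with it.
- *That all later Part 1 tests fall.* Only Tukey's step depends on this model. The tmax comparison is a separate Kruskal-Wallis test, and the Part 1 pharmacodynamic ANOVA uses treatment only.
- *That a power model is required.* For an assumed true slope of 1.10 over 0.2 to 50 mg/kg and an assumed between-subject CV of 30%, a slope test has 81% power against 52% for the one-way F-test at two-sided 5%, or 89% against 67% at 10%. That ranking depends on the log-linear shape. If instead the 2 and 10 mg/kg means alone depart by +0.5 on the ln scale, simulation at CV 30% and 5% gives about 1% for the slope test and 72% for the F-test. The Protocol supplies neither a slope nor a CV, and ANOVA on dose-normalised parameters is a legitimate choice.

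**Conclusion.** The Part 1 dose-proportionality model is wrong as written. It contradicts the parallel single-dose design stated in the same synopsis. Dose within cohort has 0 df with five or six cohorts, the subject variance is not identifiable, and the condition for Tukey's comparisons cannot be met by the model as specified. The conclusion rests on two facts in the Protocol, one dose level per cohort and one administration per subject, and on no assumed variance or effect size. The permitted dose adaptations do not change it.

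The weight is moderate. Seven listed parameters under a secondary objective are affected, and the information needed to answer the question is all still there.

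**What to change.** Replace the Part 1 PK model with a fixed-effects one-way ANOVA of the same ln-transformed parameters on dose alone, with no cohort term and no random subject term. State that Tukey's comparisons follow a significant dose effect in that model. The degrees of freedom are 4 and 15 with five cohorts, and 5 and 18 with six distinct doses. The same wording also covers a repeated dose, where the two cohorts at that dose are pooled.

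A power-model slope with its 90% confidence interval could be reported as a supplementary summary, but it is optional and not part of the correction.

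The cost is one paragraph in the Protocol and the matching text in the analysis plan. No extra data, subjects or visits are needed.

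### The SAD dose-proportionality analysis is a significance-gated ANOVA on 4 active subjects per dose, with no interval estimate of departure from proportionality for Cmax, C72h or the AUCs

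*Protocol*

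**What the plan says.** Under Statistical Methods, Pharmacokinetics, the protocol fixes the method for Part 1: "proportionality between the dose administered and the PK parameters will be assessed by means of a mixed-effects analysis of variance (ANOVA) model". Its terms are fixed effects for cohort and for the dose inside each cohort, plus a random effect for the subject. The listed responses include dose-normalised Cmax, C72h, AUC0-72h and AUCinf, all ln-transformed. The next step is conditional: "In case of significant dose effect observed on these parameters, comparison between doses will be performed using Tukey's test".

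For these parameters the section names no exponent, no confidence interval and no criterion for proportionality. The only SAD pharmacokinetic interval it names is a 90% interval for pairwise tmax comparisons, and that too follows only a significant overall test. No alpha is stated for the dose effect.

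The Part 1 table gives the numbers: "Two sentinel subjects will be dosed, followed by 4 subjects 24h later", allocated 1:1 and 3:1 active to placebo. Each dose therefore has 1 + 3 = 4 active subjects. The fixed doses are 0.2, 2, 10, 25 and 50 mg/kg; the optional sixth cohort has no fixed dose. Under Sample size, "no formal sample size calculations have been performed for both parts of the clinical study". Pharmacokinetics is a secondary objective.

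**The concern.** Proportionality is a question of size: by how much does exposure depart from a constant multiple of dose? The specified analysis asks instead whether five group means differ. It ignores the order and spacing of the doses, and spends 4 degrees of freedom on what may be mainly a one-parameter question. If the F-test is not significant, the described procedure stops without a measure of how far from proportional the data could still be. With 4 subjects per dose, a non-significant result is compatible with a considerable departure. A secondary objective could then end without a usable answer, although the same 20 subjects can supply an estimate with an interval.

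This is separate from the nesting in the stated model. Each SAD cohort has one dose, so dose within cohort adds nothing once cohort is fitted, and with one value per subject the random subject term cannot be separated from the residual. Repairing that gives a one-way ANOVA on dose, and the point made here applies to that repaired model.

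**Working it through.** The protocol gives no power, alpha or variability for this analysis, so there is no stated figure to reproduce.

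**Inputs from the protocol.** Doses 0.2, 2, 10, 25 and 50 mg/kg; 4 active subjects each, 20 in total; range 50/0.2 = 250-fold.

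**Assumptions (not in the protocol).** Two-sided alpha 0.05. Between-subject SD of the ln parameter 0.3, range 0.2 to 0.4. True exponent 1.1, which makes dose-normalised exposure drift by 250^0.1 = 1.74-fold across the range. The model is read as a one-way ANOVA on dose.

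**Step 1, spread of the doses.** The ln doses are −1.609, 0.693, 2.303, 3.219 and 3.912, with mean 1.703. The squared deviations sum to 19.53, so Sxx = 4 × 19.53 = 78.1.

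**Step 2, log-linear drift.** The noncentrality is λ = δ² × Sxx / σ², where δ is the exponent minus 1. At SD 0.3, λ = 0.01 × 78.1 / 0.09 = 8.68. The F-test uses noncentral F(4, 15) with critical value 3.06. The slope test uses noncentral t(18) with noncentrality √8.68 = 2.95 and critical value 2.10.

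| SD | F-test power | F-test misses | Slope power | Slope misses |
|---|---|---|---|---|
| 0.2 | 87% | 13% | 99% | 1% |
| 0.3 | 50% | 50% | 80% | 20% |
| 0.4 | 29% | 71% | 55% | 45% |

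**Step 3, Tukey step.** The smallest ratio of two dose means that can be significant is exp(q/√2 × σ × √(2/4)), with q(0.95; 5, 15) = 4.37. At SD 0.3 this is exp(4.37 × 0.3 / 2) = 1.93 (1.55 to 2.40 over SD 0.2 to 0.4). At SD 0.3, an observed ratio of exactly 1.74 would therefore not be significant.

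**Step 4, what an estimate would give.** The half-width of the 90% CI for the exponent is t(0.95; 18) × σ / √Sxx = 1.734 × 0.3 / 8.84 = 0.06 (0.04 to 0.08). Over the 250-fold range this is a factor of 250^0.0589 = 1.38 either way (1.24 to 1.54).

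**Step 5, other shapes.** The same 1.74-fold departure was placed at single doses, with SD 0.3. For one dose, λ = 4 × 0.8 × (ln 1.74)² / 0.09 = 10.9, which gives the F-test 61% wherever that dose lies. Slope power is by simulation.

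| Departure at | F-test | Slope test |
|---|---|---|
| 0.2 mg/kg only | 61% | 69% |
| 10 mg/kg only | 61% | 3% |
| 25 mg/kg only | 61% | 12% |
| 50 mg/kg only | 61% | 28% |
| 25 and 50 mg/kg | 80% | 74% |

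The slope test gains for a log-linear drift and for a departure at the lowest dose. It loses in the other patterns, badly when a single middle dose departs.

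**Step 6, price of two tests.** Under exact proportionality, slope and lack-of-fit tests each at 5% give at least one false signal with probability about 1 − 0.95² = 9.75%, so about 10%.

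**The case against.** Three stronger readings are tempting, and the document does not support them.

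- **A non-significant result will be declared proportional.** A reader might infer this from the gate. The protocol says only what follows a significant dose effect; it gives no rule for the other case and makes no claim of proportionality.
- **A 1.7-fold drift is missed about half the time, as a fact of the plan.** The SD, the alpha and the 1.74-fold target are all assumptions. At a CV of 30% (SD 0.294), raising alpha to 0.10 lowers the F-test's miss rate for a 1.7-fold drift from 52% to 37%.
- **Regression is simply the more powerful method.** Step 5 shows otherwise. Ignoring dose order makes the ANOVA indifferent to which dose departs, and the protocol gives no ground for expecting a log-linear departure.

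Beyond these, ANOVA on dose-normalised parameters is a recognised analysis, and its group geometric means and ratios carry information about departure even though their reporting is not described. Low power is no error in itself in a first-in-human study whose numbers are declared to be practical. A statistical analysis plan that is not at hand may add an exponent and interval.

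All of this limits the point but does not remove it. The protocol does not leave the method open: it names a test with a conditional follow-up. Small groups are a reason to estimate rather than to gate on significance.

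**Conclusion.** The point stands as a worthwhile, cheap improvement to a method that the protocol fixes. It is not a contradiction or a misstatement. For Cmax, C72h and the AUCs the specified SAD analysis gives no interval estimate of departure from proportionality, and a non-significant F-test would leave the question unanswered. That holds at any SD.

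The size is conditional. With alpha 0.05 and a log-linear 1.74-fold drift, the F-test misses it 50% of the time at SD 0.3 (13 to 71% over SD 0.2 to 0.4), against 20% (1 to 45%) for the slope. When only the top dose or only the 10 mg/kg dose departs, the slope test has 28% and 3% power against 61% for F at SD 0.3. The exponent should therefore be added to the ANOVA, not put in its place.

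**What to change.** In Statistical Methods, Pharmacokinetics (SAD part):

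- Add, as the main estimate of proportionality, a power model: regression of ln(Cmax), ln(C72h), ln(AUC0-72h) and ln(AUCinf) on ln(dose). Report the exponent with its 90% CI and the implied fold-departure over the dose range.
- Add a lack-of-fit test, so that a departure confined to one dose is not overlooked.
- Keep the ANOVA, written as a one-way model on dose, and the dose-normalised geometric means as the check that does not depend on shape.
- State that a non-significant ANOVA does not establish proportionality.

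The cost is wording and one regression per parameter on data already planned. There are two drawbacks. The exponent assumes log-linearity, which the lack-of-fit test and the ANOVA check only in part with 20 subjects. Running slope and lack-of-fit tests together raises the chance of at least one false signal to about 10%, so the conclusion should rest on the interval.

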##### Pharmacodynamics

- In the SAD part, percent change at each postdose time point for IgG, AUECs and  $E_{\max}$  will be compared between the treatment groups (placebo subjects pooled) using an ANOVA model with treatment as fixed effect. In case of a significant treatment effect, pairwise comparison between treatments will be performed using Tukey's test.  
As  $t_{E_{\max}}$  is a discrete variable dependent on selected blood sampling times, comparison between treatment groups (placebo subjects pooled) will be assessed using a non-parametric Kruskal-Wallis test and in case statistically significant, applying Wilcoxon's rank sum test with Moses' 90% CIs for pairwise comparisons.

- 
- In the MAD part, percent change at each postdose time point for IgG, AUECs and  $E_{\max}$  will be compared, when appropriate, between the treatment groups (placebo subjects pooled), separately for each administration day, using an ANOVA model with treatment as fixed effect. In case of a significant treatment effect, pairwise comparison between treatments will be performed using Tukey's test.

As  $t_{E_{\max}}$  is a discrete variable dependent on selected blood sampling times, comparison between treatment groups (placebo subjects pooled) will be assessed using a non-parametric Kruskal-Wallis test, with pairwise comparisons using Wilcoxon's rank sum test plus 90% CIs (only in case the overall dose effect is statistically significant). The day effect will be tested using the non-parametric Wilcoxon's signed ranks test.

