#### Pharmacodynamics

Pharmacodynamic assessments will be conducted for the SAD and MAD studies to measure for the total immunoglobulin G (IgG), IgG subtype (IgG 1, IgG 2, IgG 3, and IgG 4), IgA, IgD, IgE and IgM levels.

The PD effect will be measured by endogenous immunoglobulin concentration versus baseline change (in %). The following parameters will be calculated, where appropriate, from individual data of total IgG, IgG subtypes (1, 2, 3, and 4), IgA, IgD, IgE, IgM change from baseline:  $E_{\max}$ ,  $t_{E_{\max}}$ , and AUEC.

Unlike total IgG and IgG subtype levels, no changes in IgA, IgD, IgE, IgM levels are to be expected based on FcRn biology and pre-clinical data. As such, the abovementioned parameters will only be calculated for these types of immunoglobulins if a PD effect is observed.

The relationship between ARGX-113 concentration and total IgG or IgG subtypes 1, 2, 3, and 4, change from baseline values will be graphically presented. If appropriate, graphical relationship between main PK and PD parameters will also be assessed.

The PK/PD relationship will be assessed graphically.

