#### Safety

- The following safety parameters will be tabulated and analyzed descriptively: adverse events, clinical laboratory tests, ECGs, physical examinations, and vital signs.
-

### TIME AND EVENTS SCHEDULE: PART 1

Time of Visit (days)	Screening a	Day -1	Day 1		Day 2	Day 3	Day 4	Day 5	Day 7	Day 15	Day 22	Day 29 / Follow-up Visit		
			Hours relative to start of study drug infusion											
Time From Dose			0h b	2h c	4h	8h	24h	48h	72h	96h	144h	336h	504h	672h
Informed consent d	X													
In-/exclusion criteria	X	X												
Medical history/ concomitant diseases	X													
Demographic data	X													
Physical examination	X e	X e	X g				X			X				X
Vital signs f	X	X	X g	X	X	X	X		X	X	X	X	X	X
Single 12-lead ECG	X	X	X g	X	X	X	X		X	X	X	X	X	X
Clinical laboratory tests h	X		X g				X	X	X	X	X	X	X	X
Serum albumin determination			X g	X	X	X	X	X	X	X	X	X	X	X
Lymphocyte typing: B, T subset and NK cells	X		X g	X	X	X	X		X		X	X	X	X
Urinalysis	X		X g				X		X	X	X	X	X	X
Pharmacokinetics: Blood			X g	X	X	X	X	X	X	X	X	X	X	X
Pharmacokinetics: Urine collection i		X	X						X					
Pharmacodynamics j			X g	X	X	X	X	X	X	X	X	X	X	X
Anti-drug antibodies (ADA)			X g							X	X	X	X	X
Urine drug screen and alcohol breath test k	X	X												
Pregnancy test l	X	X												X
Virology/Bacterial screen m	X													
Randomization			X g											
Administration of study drug n			X											
Confinement		Check-in								Check-out o				
Concomitant therapies p	X													X
Adverse events p	X													X

a. To take place between 1 and 28 days prior to

administration of study drug.

b. 0h represents the start of infusion of study drug.

- c. Assessments to take place immediately following end of study drug infusion.
- d. No study-related assessment is to be carried out before signing of the informed consent form.
- e. Includes weight, height and BMI at screening and weight only on Day-1.
- f. Blood pressure and pulse rate (supine) and oral body temperature.
- g. Assessments should be completed pre-dose.

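### IgG percent change, AUEC and Emax are compared by treatment-only ANOVA on the raw percent scale; a log-ratio analysis with baseline IgG as covariate would be a low-cost improvement of uncertain size

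*Protocol*

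**What the plan says.** Under Statistical Methods, Pharmacodynamics, the SAD responses (IgG percent change at each postdose time point, AUECs and Emax) "will be compared between the treatment groups (placebo subjects pooled) using an ANOVA model with treatment as fixed effect", with Tukey comparisons if the treatment effect is significant. The MAD responses are compared in the same way, "separately for each administration day, using an ANOVA model with treatment as fixed effect". No covariate and no transformation is named in either part.

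Baseline does enter the response. Under Criteria for Evaluation, the PD effect is defined as percent change versus baseline, and Emax and AUEC are calculated "from individual data of total IgG, IgG subtypes (1, 2, 3, and 4), IgA, IgD, IgE, IgM change from baseline". In the Part 1 Time and Events Schedule, the only PD sample before dosing is the one at 0h, with the footnote "g. Assessments should be completed pre-dose". The Part 2 schedules likewise have no PD sample at screening or Day -1.

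On size, the overview states: "The SAD study will contain up to 6 cohorts of 6 subjects each" and "The MAD study will contain up to 4 cohorts of 8 subjects each". PD is a secondary objective, and "no formal sample size calculations have been performed for both parts of the clinical study".

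**The concern.** Two features of the model deserve attention.

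- **Baseline is only a denominator.** Measurement error and day-to-day variation in one pre-dose sample pass into every percent change derived from it. A covariate can remove part of that noise, and the value is already collected.
- **The scale is raw percent.** If IgG varies by a roughly constant proportion, percent change has a smaller spread in a group whose IgG has fallen far than in placebo. A single ANOVA error variance averages over these unequal spreads. The same section ln-transforms the PK parameters but leaves the PD responses untransformed.

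At stake are the precision and calibration of the reported PD dose-response comparison, a secondary objective with 4 active subjects per SAD dose and 6 per MAD cohort.

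**Working it through.** The protocol states no power, SD or precision for PD, so there is no figure to reproduce.

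**Group sizes (Parts 1 and 2 design tables).** Each SAD cohort is 1:1 plus 3:1, so 4 active and 2 placebo. Five cohorts give 5×4 + 10 = 30 subjects in 6 groups, error df 24. Six cohorts give 6×4 + 12 = 36 in 7 groups, df 29. Each MAD cohort is 6:2, so four cohorts give 4×6 + 8 = 32 in 5 groups, df 27.

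**Effect of a baseline covariate.** Let rho be the within-group correlation of the change with baseline. It is an assumption, shown as a range. The expected variance ratio of a pairwise difference, with versus without the covariate, is (1 − rho²) × (1 + 1/(df − 2)). The CI-width ratio is its square root times t(0.975, df − 1)/t(0.975, df). For SAD with five cohorts the second factor is 1 + 1/22 = 1.045.

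| abs(rho) | SAD 5 cohorts: variance | SAD 5: CI width | SAD 6: CI width | MAD 4 cohorts: CI width |
|---|---|---|---|---|
| 0 | 1.045 | 1.025 | 1.020 | 1.022 |
| 0.2 | 1.004 | 1.004 | 0.999 | 1.001 |
| 0.3 | 0.951 | 0.978 | 0.973 | 0.975 |
| 0.5 | 0.784 | 0.888 | 0.883 | 0.885 |
| 0.7 | 0.533 | 0.732 | 0.728 | 0.730 |

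A simulation of the variance ratios (6,000 runs per case) agrees within about 0.02. Break-even is at |rho| of about 0.2.

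The MAD column assumes that all four cohorts contribute. Where fewer do, the df cost is larger. With Cohorts 9 and 10 only, there are 4 + 6 + 6 = 16 subjects and df 13, and the factor is 1 + 1/11 = 1.09.

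**What rho might be.** Assume a 50% proportional fall independent of baseline, between-subject log-SD 0.15 to 0.30, within-subject or assay log-SD 0.03 to 0.10, and response log-SD 0.05 to 0.10. Percent change then correlates with baseline at about −0.03 to −0.36. That runs from a small loss of precision to a CI about 5% narrower.

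**Effect of the scale.** Assume the log ratio has the same SD, s, in every group, and that every dose group keeps a fraction k of its baseline IgG. The percent-change SD is then proportional to s on placebo and to ks on active.

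- SAD, five cohorts: pooled variance is (9 + 15k²)/24 × s², against a true active variance of k²s². With no fall (k = 1) they agree. With a 50% fall (k = 0.5) the pooled value is (9 + 3.75)/24 = 0.53 against 0.25. Dose-versus-dose standard errors are too large by a factor √(0.53/0.25) = 1.46.
- SAD, six cohorts, k = 0.5: (11 + 18×0.25)/29 = 0.534, factor 1.46.
- MAD, four cohorts, k = 0.5: (7 + 20×0.25)/27 = 0.444, factor √(0.444/0.25) = 1.33.
- Dose versus placebo, k = 0.5: in SAD the variance used is 0.531 × (1/4 + 1/10) = 0.186, against a true 0.25/4 + 1/10 = 0.1625, so the standard error is about 7% too large. In MAD it is 0.444 × (1/6 + 1/8) = 0.130 against 0.25/6 + 1/8 = 0.167, so about 12% too small.

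Under this assumption the log ratio has equal variance in all groups, and these errors disappear.

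**The case against.** One-factor ANOVA on percent change is a valid analysis. Baseline is already used, PD is secondary, and no power claim is undermined. All of that stands. The pooled placebo group (10 to 12 in SAD, 8 in MAD) and an error variance on 24 or more df also mean that small active groups do not by themselves imply a large loss.

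Four stronger readings are tempting, and the document does not support them.

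- **That precision is certainly being wasted.** This needs |rho| above about 0.2, and the document gives no correlation.
- **That the gain can be read from (1 + r)/2, with r the correlation of baseline and follow-up.** This formula assumes equal variances and no differences in drug response. Take assumed log-SDs of 0.30 between subjects, 0.10 within subjects and 0.15 for response. Then r = 0.09/√(0.10 × 0.1225) = 0.81, and the formula promises a 9% variance reduction. The true reduction is 0.001/0.0425 = 2.4%, which is less than the 4.5% df cost in SAD.
- **That chance baseline imbalance biases the comparison.** It adds variance, which the ANOVA standard error largely reflects already. Cohorts are sequential, so doses are not randomised against each other, but nothing in the document points to a systematic baseline difference.
- **That the judgement of an IgG plateau or the choice of doses is affected.** The Safety Committee works from blinded data, and the MAD doses were set from blinded results. The ANOVA separates treatment groups and pools placebo, so it needs unblinded allocation. Nothing says that it feeds those decisions.

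The scale argument also rests on its assumption. With the log-SDs just given, placebo variance on the log scale is 2 × 0.10² = 0.02 and active variance 0.0425. At a 50% fall the percent scale gives a pooled variance of (9×0.02 + 15×0.0106)/24 = 0.0141 against 0.0106, so SAD dose-versus-dose standard errors are about 15% too large. The log scale gives (9×0.02 + 15×0.0425)/24 = 0.0341 against 0.0425, so they are about 10% too small. The log scale is then closer, but not exact.

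**Conclusion.** The point holds as a recommended improvement to a secondary analysis. It is not an error or a contradiction. Because the protocol writes the model out, it is also more than a detail left to the SAP.

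The scale is the firmer part. With constant log-SD and a 50% fall in every dose group, dose-versus-dose standard errors are about 46% too large in SAD and 33% too large in MAD. The misstatement vanishes with no fall and shrinks if subjects differ in response.

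The covariate is inexpensive insurance with an uncertain return. At an assumed |rho| of 0.3 it narrows intervals by 2 to 3%, and at 0.5 by 11 to 12%; below about 0.2 it slightly widens them. The consequence is confined to the reported PD dose-response comparison.

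**What to change.** In both SAD and MAD:

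- For each time point, analyse ln(post/baseline) IgG with treatment and ln(baseline IgG) in the model, and back-transform to percent change.
- Analyse Emax on the log-ratio scale with baseline IgG as covariate.
- Add baseline IgG as a covariate for AUEC. This does not address unequal spread in AUEC, so inspect residual spread by group there.

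The change should be made before unblinding. It needs no new data or visits. It costs 1 df per model: intervals up to about 2.5% wider with all cohorts in the model if baseline is unrelated to change, and somewhat more on MAD administration days to which fewer cohorts contribute.
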